10.12.8.2. Home Health Visits for Substudy B

A home healthcare service may be utilized to facilitate scheduled visits. Home health visits include a healthcare provider conducting an in-person study visit at the participant's location, rather than an in-person study visit at the site. The following may be performed during a home health visit (see the SoA):

 Procedures as indicated for Visits 202, 203, and 204 (see Section 10.12.8.9.3, Section 10.12.8.9.4, and Section 10.12.8.9.5, respectively).

10.12.8.3. Immunogenicity Assessments for Substudy B

Samples will be collected at the time points specified in Section 10.12.1 from all participants, and the following assays will be performed:

- HAI titers against seasonal strains (CCI), (CCI), and (CCI) recommended by WHO.
- SARS-CoV-2 neutralization assay (reference strain).
- SARS-CoV-2 neutralization assays (Omicron BA.4, Omicron BA.5, and other emerging variants [under monitoring, of interest, and/or of concern], including other Omicron sublineages, may also be evaluated).

10.12.8.3.1. N-Binding Antibody Test for Substudy B

The N-binding antibody test will be performed by the central laboratory on each blood sample to establish prior exposure to SARS-CoV-2 up to each time point. These data will be used for study analyses.

10.12.8.4. Biological Samples for Substudy B

See Section 8.2.1.

10.12.8.5. Safety Assessments for Substudy B

See Section 8.3.

10.12.8.5.1. ECGs for Substudy B

ECGs will be collected at the times specified in Section 10.12.1 for Substudy B.

All scheduled 12-lead ECGs should be performed after the participant has rested quietly for at least 10 minutes in a supine position. The ECGs should be obtained prior to blood collection, measurement of blood pressure, and measurement of pulse rate. ECGs will be performed in triplicate.

ECG data will be submitted to a central laboratory for evaluation. The final ECG report from the central laboratory should be maintained in the participant's source documentation and be the final interpretation of the ECG recording. Any clinically significant changes from the baseline/Day 1 ECG may potentially be AEs (see Section 10.3) and should be evaluated further, as clinically warranted.

In some cases, it may be appropriate to repeat abnormal ECGs to rule out improper lead placement as contributing to the ECG abnormality. It is important that lead placement be in the same position each time during each assessment visit in order to achieve precise ECG recordings.

ECG abnormalities consistent with probable or possible myocarditis or pericarditis are those judged as such by a cardiologist, including:

- Sustained atrial or ventricular arrhythmias
- Second-degree Mobitz Type II or worse AV block, new bundle branch block
- Diffuse ST-segment elevation or PR-segment inversion, compatible with pericarditis

Echocardiograms may be performed as detailed in Section 10.12.8.10.

ECG values of potential clinical concern are listed in Section 10.9.

10.12.8.6. Clinical Safety Laboratory Assessments for Substudy B

Please see Section 8.3.4. Additionally, see Section 10.2 for the list of clinical safety laboratory tests to be performed and the SoA for the timing and frequency.

10.12.8.7. Stopping Rules for Substudy B Groups 2, 6, 7, 8, 9, 10, 11, and 12

The following stopping rules are in place for participants receiving one of the following combinations, not previously covered in Substudy A: qIRV/bivalent BNT162b2 (original/Omi BA.4/BA.5), tIRV/bivalent BNT162b2 (original/Omi BA.4/BA.5), or bIRV/bivalent BNT162b2 (original/Omi BA.4/BA.5) concurrently with licensed QIV in Substudy B, based on AE, ECG, and laboratory data review. These data will be reviewed on an ongoing basis by the investigator (or medically qualified designee) and sponsor in order to promptly identify and flag any event that potentially contributes to a stopping rule.

The sponsor study team will be unblinded, so will be able to assess whether or not a stopping rule has been met on the basis of a participant's individual study intervention allocation.

In the event that sponsor personnel confirm that a stopping rule is met, the following actions will commence:

- The IRC will review all appropriate data.
 - The stopping rule will PAUSE randomization and study intervention administration in all vaccine groups across both age strata
 - For all participants already vaccinated, all other routine study conduct activities, including ongoing data entry, reporting of AEs, participant e-diary completion, blood sample collection, and participant follow-up, will continue during the pause.

A stopping rule is met if any of the conditions listed in the stopping rule criteria below occur within 4 weeks after study intervention administration. Each vaccine group will be evaluated for contribution to stopping rules independently.

Stopping Rule Criteria:

- If any vaccinated participant develops:
 - A new ECG abnormality that a cardiologist judges consistent with probable or possible myocarditis or pericarditis, including but not limited to:
 - Sustained atrial or ventricular arrhythmias
 - Second-degree Mobitz Type II or worse AV block, new bundle branch block
 - Diffuse ST-segment elevation or PR-segment inversion, compatible with pericarditis
 - An abnormal troponin I value that is confirmed abnormal on repeat testing, assessed as related to study intervention by the investigator.
- If ≥1 vaccinated participant develops a confirmed clinical diagnosis of myocarditis or pericarditis.
- If any vaccinated participant dies.
- If ≥1 vaccinated participant experiences a Grade 4 unsolicited AE, or SAE of any severity, assessed as related by the investigator.

5. If ≥2 participants vaccinated with qIRV/bivalent BNT162b2 (original/Omi BA.4/BA.5), tIRV/bivalent BNT162b2 (original/Omi BA.4/BA.5), or bIRV/bivalent BNT162b2 (original/Omi BA.4/BA.5) given concurrently with licensed QIV, at the same dose level, develop the same or similar Grade 3 or higher unsolicited AE, other than myocarditis/pericarditis, assessed as related to study intervention by the investigator. Note that the local reactions, systemic events, and fever specified in Section 8.3.5, reported within 7 days from the day of administration of the study intervention, irrespective of whether they are recorded in the e-diary or as AEs, are excluded from this stopping rule.

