Enrollment of participants 18 through 64 years of age will occur only during Substudy B. During Substudy B (Groups 2, 6, 7, 8, 9, 10, 11, and 12), the enrollment will be controlled such that no more than 10 participants (considered sentinel participants) can be vaccinated on the first day; vaccination of the remaining participants will commence no sooner than 24 hours after this safety pause.

Stopping rules will apply to the groups receiving the novel-exploratory combinations of bivalent BNT162b2 (original/Omi BA.4/BA.5) with qIRV, tIRV, and bIRV, as detailed in Section 10.12.8.7.

Safety data accumulated at least 4 weeks following vaccination of participants 18 through 64 years of age in Substudy B will be reviewed by the sponsor's IRC, and if these data are deemed acceptable, the IRC will evaluate which groups (as detailed in Table 2) are acceptable for further study.

Immunogenicity Blood Draws in Substudy B:

Blood samples of approximately 15 mL will be collected for immunogenicity assessments prior to vaccination and at 4 weeks after vaccination. Up to 20 participants in Groups 3, 4, and 5 for the 18- through 64-year age stratum will be asked to consent to alternatively providing 50-mL, rather than 15-mL, blood samples at the same time points, which will be used for immunogenicity assessments as well as assay development/maintenance.

For Substudy B blood draws (as detailed above), up to the first 20 participants who are enrolled first, and who consent, will have the higher-volume blood draws of 50 mL.

All participants will be asked to complete a reactogenicity e-diary for 7 days following each vaccination.

Following vaccination, AEs will be collected from informed consent signing through 4 weeks following each vaccination, and SAEs will be collected from informed consent signing through 6 months after the first vaccination. In addition, AEs will be collected that occur up to 48 hours after blood draws.

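### Stopping-rule criterion 5 in Substudy B cannot be triggered by Group 12 (qIRV alone), although the section heading lists that group

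*Protocol*

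**What the plan says.** Protocol section 10.12.8.7 is headed "Stopping Rules for Substudy B Groups 2, 6, 7, 8, 9, 10, 11, and 12". Table 2 shows that Group 12 gets qIRV with neither bivalent BNT162b2 nor licensed QIV, in about 30 participants.

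The text under that heading is narrower. The lead-in opens "The following stopping rules are in place for participants receiving one of the following combinations, not previously covered in Substudy A" and then lists three products, each of them an influenza modRNA vaccine combined with bivalent BNT162b2. Criterion 5 carries the same list inside the criterion: "If ≥2 participants vaccinated with qIRV/bivalent BNT162b2 (original/Omi BA.4/BA.5), tIRV/bivalent BNT162b2 (original/Omi BA.4/BA.5), or bIRV/bivalent BNT162b2", the last of these with licensed QIV. Section 10.12.4.1 says "Stopping rules will apply to the groups receiving the novel-exploratory combinations of" bivalent BNT162b2 with qIRV, tIRV and bIRV.

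Criteria 1 to 4 name no product. Criterion 4, for example, reads "If ≥1 vaccinated participant experiences a Grade 4 unsolicited AE, or SAE of any severity, assessed as related by the investigator". A met rule will "PAUSE randomization and study intervention administration in all vaccine groups". On counting, the section says "Each vaccine group will be evaluated for contribution to stopping rules independently".

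The sentinel provision in 10.12.4.1 uses the heading's list: "Groups 2, 6, 7, 8, 9, 10, 11, and 12), the enrollment will be controlled such that no more than 10 participants" may be vaccinated on the first day. Schema note b (section 1.2) exempts only Groups 1, 3, 4 and 5 from the sentinel review. The synopsis applies the stopping rules to all groups, deferring to the protocol for detail. The Substudy B SAP sets out no stopping rules, so it does not settle the scope.

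**The concern.** A stopping rule should have one reading before an event occurs. Here the heading names a group that the product lists below it leave out. Sponsor staff must confirm from a participant's allocation whether a rule has been met, and for a Group 12 participant the text they would apply conflicts.

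What is at stake is the formal pause, which halts randomization and dosing in every vaccine group. If a repeated Grade 3 reaction appeared in Group 12, the rule written for that pattern would not respond. Because groups are evaluated separately, Group 12 cases would not be counted through another group.

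**Working it through.** **Step 1: scope, text by text.** All of the wording below is current and legible; none of the conflict comes from redaction.

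| Place in the protocol | Group 12 (qIRV alone) |
|---|---|
| 10.12.8.7, heading | named |
| 10.12.4.1, sentinel list | named; same eight groups as the heading |
| 1.2, schema note b | not among the exempt groups (1, 3, 4, 5) |
| 1.1, synopsis | falls under all groups |
| 10.12.8.7, criteria 1 to 4 | no product restriction |
| 10.12.8.7, lead-in | not among the products |
| 10.12.8.7, criterion 5 | not among the products |
| 10.12.4.1, scope of the stopping rules | not among the products |

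The sentinel list and note b concern the sentinel pause rather than the stopping rules, so they are supporting evidence only. The Amendment 4 entry in Appendix 13 describes the section, when it was added, as covering the new exploratory groups and gives the same eight numbers. It is cited here for intent only. On balance inclusion is the better-supported reading.

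**Step 2: what Group 12 can trigger if it is included.**

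- Criterion 1 (ECG abnormality, or confirmed and related troponin abnormality): yes.
- Criterion 2 (confirmed myocarditis or pericarditis): yes.
- Criterion 3 (death): yes.
- Criterion 4 (one related Grade 4 unsolicited AE, or one related SAE): yes.
- Criterion 5 (two or more participants with a similar related unsolicited AE of Grade 3 or above): no, because the product list inside the criterion omits qIRV alone.

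Criterion 5 also sets aside the prompted local reactions, systemic events and fever reported within 7 days. Removing those, and what criteria 1 to 4 already catch, leaves one pattern uncovered: the same kind of related, non-serious Grade 3 unsolicited AE in at least two Group 12 participants.

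**Step 3: size in participants (Table 2 planned numbers).**

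- Groups in the heading: 8 × 30 = 240.
- Groups reached by criterion 5: 7 × 30 = 210.
- Group 12: 240 − 210 = 30, and 30/240 = 12.5%.

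**Step 4: illustration, assumption only.** The documents give no rate for such an AE, and the point does not depend on one. As a check on method, Table 9's chance of at least one event in 30 at a true rate of 1% is 1 − 0.99^30 = 26.0%, which reproduces. The chance of at least two in n is 1 − (1−p)^n − n·p·(1−p)^(n−1).

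| Assumed true rate p | n = 30 (whole group) | n = 10 (sentinel maximum) |
|---|---|---|
| 1% | 3.6% | 0.4% |
| 2% | 12.1% | 1.6% |

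The n = 30 column is an upper bound at each rate, because a pause matters only while some group is still being dosed. The documents do not say how much dosing remained at Amendment 6.

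**The case against.** The strongest reply is that the practical gap is small. If Group 12 is included, the gravest events are already covered by criteria 1 to 4. Group 12 has the sentinel limit and 24-hour pause, and scheduled ECG and troponin checks at Visits 202 and 203. Sponsor staff are unblinded (10.12.6.2.3) and the IRC monitors safety throughout (10.1.5.1). qIRV alone is also the better-known product: it was given in Substudy A and is in a Phase 3 study whose independent monitoring committee endorsed continued enrollment (2.2.3.2). All of this stands and limits the consequence. None of it makes criterion 5 apply to Group 12. The ECG and troponin checks address other criteria, and a repeated non-serious Grade 3 AE is left to judgment instead of a rule.

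A reader might infer something stronger from the lead-in: that Group 12 is outside all five criteria, so that even a death there would not trigger the formal pause. Substudy A might seem to support this, since its rules (10.11.8.6) cover combination groups only and let qIRV-alone dosing continue during a pause. A literal reading of the lead-in does lead there, which is a reason to repair it. The documents do not support it as the intended scope. It would empty the heading of a group it lists by number, and it sits badly with the synopsis, the Amendment 4 entry and criteria worded for any vaccinated participant. The Substudy A carve-out belongs to another substudy, whose pause is confined to combination groups at the affected and higher dose levels. Substudy B has no such carve-out and pauses every group.

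A reader might also apply the higher rates in Table 9 (5% or 7%) and infer that a missed signal is likely. That table concerns any particular AE. Nothing in the documents supports those rates for a related, non-serious Grade 3 AE outside the prompted reactions.

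**Conclusion.** The inconsistency is certain. Its consequence is narrow. Taking Group 12 as included, one of five criteria fails for one of eight listed groups, about 30 of 240 planned participants. The failure is confined to repeated, similar, related, non-serious Grade 3 unsolicited AEs. In the other seven groups the second such case at the same dose level triggers the pause; in Group 12 no number of cases does.

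This rests on two things: the reading of intent in step 1, which the documents favor without stating it outright, and criterion 5 being applied as written. No event rate is assumed. Because this is a participant-safety rule that halts dosing in every group, it should be corrected, but it does not show that Group 12 lacks safety oversight.

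**What to change.** Add qIRV alone (Group 12) in three places: the lead-in of 10.12.8.7, criterion 5, and the scope sentence in 10.12.4.1. In the synopsis, replace the reference to all groups with Groups 2 and 6 to 12, which also removes the implication that Groups 1, 3, 4 and 5 fall under these rules. If the sponsor in fact meant to exclude qIRV alone, the heading should drop 12 and the section should say so; leaving both versions in place is the one option to avoid.

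The cost is a change of wording at four places, but probably by substantial amendment. Stopping-rule changes in Amendments 1 and 5 were classed that way (Appendix 13), and section 10.1.1 requires ethics and health authority approval before such a change takes effect. Including Group 12 in criterion 5 also slightly raises the chance of a pause triggered by that group.

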1.2. Schema

Substudy B Schema:

Substudy B	Enrollment Co	hort 1	Enrollment Cohort 2	Enrollment Co	hort 3
Age Stratum	Vaccine groupa		Vaccine groupa 3	Vaccine groupa	
18-64 Years	(n = ~30)		(n=~≤120)	(n = ~30)	
	Vaccine group ^a 2 (n = ~30)		Vaccine group ^a 4 (n=~≤120) Vaccine group ^a 5	Vaccine group ^a 7 (n = ~30) Vaccine group ^a 8	
			(n=~≤120)	(n = ~30)	
				Vaccine group ^a 9 (n = ~30)	
				Vaccine group ^a (n = ~30)	10
				Vaccine group ^a (n = ~30)	11
				Vaccine group ^a $(n = \sim 30)$	12
	Sentine1 ^b	Full	Full	Sentinel ^b	Full
	≤10 participants	~50 participants	~330 participants	≤10 participants	~140 participants
	from group 2			per group	

- Please see Table 2 for details on the vaccine groups.
- b. A safety review will be conducted on 24 hours of postvaccination safety data from sentinel participants before full enrollment of the remaining participants in each vaccine group, with the exception of Groups 1, 3, 4, and 5, as enrollment of those groups occurred under a prior protocol version.

Note: The arrow represents the 24-hour safety pause.

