8.4.7. Adverse Events of Special Interest

The following events are considered AESIs:

For Substudy A:

- A confirmed diagnosis of influenza.
- Confirmed diagnosis of myocarditis or pericarditis occurring within 4 weeks after vaccination. See Section 10.11.8.8.10.
- Confirmed COVID-19 diagnosis after Visit 1 through the end of the study (clinical signs/symptoms per CDC²⁸ and positive SARS-CoV-2 NAAT or rapid antigen test result).

For Substudy B:

- A confirmed diagnosis of influenza.
- Confirmed diagnosis of myocarditis or pericarditis occurring within 6 weeks after vaccination. See Section 10.12.8.12.
- Confirmed COVID-19 diagnosis after Visit 201 through the end of the study (clinical signs/symptoms per CDC²⁸ and positive SARS-CoV-2 NAAT or rapid antigen test result) (excluding Group 12).
- Potential menstrual cycle disturbances. See Section 10.12.8.11.

AESIs are examined as part of routine safety data review procedures throughout the clinical trial and as part of signal detection processes. Should an aggregate analysis indicate that these prespecified events occur more frequently than expected, eg, based on epidemiological data, literature, or other data, then this will be submitted and reported in accordance with Pfizer's safety reporting requirements. Aggregate analyses of safety data will be performed on a regular basis per internal SOPs.

All AESIs must be reported as an AE or SAE following the procedures described in Section 8.4.1 through 8.4.4. An AESI is to be recorded as an AE or SAE on the CRF. In addition, an AESI that is also an SAE must be reported using the Vaccine SAE Report Form.

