- Assess systemic events (if present) in accordance with the grades provided in Section 8.3.5.3.

- Assess other findings associated with the reaction and record this on the AE page of the CRF if appropriate.
- The investigator or an authorized designee will complete the unscheduled visit assessment page of the CRF.

10.12.8.10. Additional Procedures for Monitoring of Potential Myocarditis or Pericarditis for Substudy B

Any study participant who reports acute chest pain, shortness of breath, palpitations, or any other symptom(s) that might be indicative of myocarditis or pericarditis within 6 weeks after study vaccination must be specifically evaluated in clinic by a cardiologist for possible myocarditis or pericarditis. The same applies for any participant in whom a new ECG abnormality (compared to baseline) consistent with probable or possible myocarditis or pericarditis (as listed in Section 10.12.8.5.1) or abnormal troponin I level is observed at Visit 202 or Visit 203.

In addition to a clinical evaluation, the following should be performed:

- ECG and
- Measurement of the troponin level

For any participant in whom a new ECG abnormality (compared to baseline) consistent with probable or possible myocarditis or pericarditis (as listed in Section 10.12.8.5.1) or abnormal troponin I level is observed at Visit 202 or Visit 203, this should be achieved by repeating the assessments with the central vendor(s).

If myocarditis or pericarditis is suspected based upon the initial evaluation, the following should also be performed:

- Cardiac echocardiogram and/or
- Cardiac magnetic resonance study

Details of the symptoms reported, and results of the investigations performed, will be recorded in the CRF.

Any diagnosis of myocarditis or pericarditis is considered an important medical event and must be reported as an SAE (refer to Sections 8.4.1.1 and 8.4.3). Other diagnoses should be recorded as AEs or SAEs, as appropriate. Refer also to Section 8.4.7.

10.12.8.11. Additional Procedures for Monitoring of Potential Menstrual Cycle Disturbances for Substudy B

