- Assess for other findings associated with the reaction and record these on the AE page of the CRF if appropriate.
- The investigator or an authorized designee will complete the unscheduled visit assessment page of the CRF.

10.12.8.12. Additional Procedures for Monitoring of Potential Myocarditis or Pericarditis for Substudy B

During Substudy B, participants 18 through 64 years of age will be closely monitored for potential asymptomatic and symptomatic myocarditis/pericarditis, including the use of routine ECGs and troponin testing.

Any study participant who reports acute chest pain, shortness of breath, palpitations, or any other symptom(s) that might be indicative of myocarditis or pericarditis within 6 weeks after study vaccination must be specifically evaluated in clinic by a cardiologist for possible myocarditis or pericarditis:

- Acute chest pain,
- Shortness of breath,
- Palpitations, or
- Any other symptom(s) that might be indicative of myocarditis or pericarditis.
- In addition to a clinical evaluation, the following should be performed:
- ECG and
- Measurement of the troponin level.

If myocarditis or pericarditis is suspected based upon the initial evaluation, the following should also be performed:

- Cardiac echocardiogram and/or
- Cardiac magnetic resonance study.

Details of the symptoms reported, and results of the investigations performed, will be recorded in the CRF. Any diagnosis made (eg, myocarditis, pericarditis, or other) should be recorded as an AE or SAE, as appropriate. Refer also to Section 8.4.7.

10.12.8.13. Additional Procedures for Monitoring of Potential Menstrual Cycle Disturbances for Substudy B

Any female study participant who reports any symptoms that may indicate a disturbance of their normal menstrual cycle (including, but not exclusively, heavy menstrual bleeding, amenorrhea, and irregular periods) following receipt of study intervention until 6 months after the first vaccination should be specifically evaluated by the investigator at the next planned visit. Details of the symptoms, menstrual history, and results of any investigations performed will be recorded in the CRF.

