Section 1.1: Synopsis	Clarification on the Substudy B enrollment strategy for both initial and expanded phases	Enrollment of the participants 18 through 64 years of age and safety review prior to enrolling the participants ≥65 years of age	Substantial
Section 1.1: Synopsis	Updated the number of participants	To align with the updated enrollment strategy	Substantial
Section 1.1: Synopsis	Exclusion criteria were added to Substudy B	To bring clarity	Substantial
Section 1.1: Synopsis	Substudy B study arm table was updated	To reflect XBB.1.5, placebo, and comparator	Substantial
Section 1.2: Schema	Schema was updated	To reflect the new enrollment strategy and safety review	Substantial
Section 2.1: Study Rationale	Text was edited	To align with the study design	Substantial
Section 2.2: Background	Text and references were revised	To align with the study design	Substantial
Section 2.2.3: Clinical Overview	Text was edited	To align with the study design	Substantial
Section 2.3: Benefit/Risk Assessment	Text was edited	To align with the study design	Substantial
Section 4.3: Justification for Dose	Text was edited; addition of BNT162b2 (Omi XBB.1.5)	To align with the study design	Substantial
Section 6: Study Intervention(s) and Concomitant Therapy	Text was edited; more details were added	To bring clarity on the vaccine groups	Substantial
Section 6: Study Intervention(s) and Concomitant Therapy	Text was edited; Table 2 was edited and split into 2 tables (now Tables 2 and 3); previous Tables 3 and 4 were removed	To bring clarity on the vaccine groups	Substantial
Section 7.1: Discontinuation of Study Intervention	Details were added for participants in Group 14 or 15 who may discontinue study intervention administration	To align with the addition of 2-dose groups	Nonsubstantial

Section # and Name	Description of Change	Brief Rationale	Substantial or Nonsubstantial
Section 8.3.5: Electronic Diary	entries should be included in the AE	To align with regulatory	Nonsubstantial
Section 8.4.1: Time Period and Frequency for Collecting AE and SAE Information	CRF Text added to details of AE collection requirements for participants receiving 2 doses of study intervention	To ensure adequate safety follow-up for those who receive 2 doses	Substantial
Section 8.4.7: Adverse Events of Special Interest	Myocarditis and pericarditis are now considered AESIs for up to 6 weeks (previously 4 weeks) after vaccination	To align with regulatory requirements for COVID-19 vaccines	Substantial

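### Substudy B: confirmed myocarditis or pericarditis is an adverse event of special interest for 6 weeks, but a case pauses dosing automatically only within 4 weeks (low priority)

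*Protocol*

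**What the plan says.** Section 10.12.8.7 of the protocol sets the Substudy B stopping rules for Groups 2 and 6 to 12. Its lead-in says a rule is met if any of the conditions in the "criteria below occur within 4 weeks after study intervention administration". One of the conditions is that at least one "vaccinated participant develops a confirmed clinical diagnosis of myocarditis or pericarditis". It carries neither a separate time window nor a relatedness test. When a rule is met, the IRC reviews the data and dosing stops: "The stopping rule will PAUSE randomization and study intervention administration in all vaccine groups across both age strata".

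Other Substudy B sections use 6 weeks for the same event:

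- Section 8.4.7 lists as an AESI "Confirmed diagnosis of myocarditis or pericarditis occurring within 6 weeks after vaccination".
- Sections 10.12.8.10 and 10.12.8.12 say that symptoms suggesting either condition "within 6 weeks after study vaccination must be specifically evaluated in clinic by a cardiologist".
- Section 10.12.8.10 adds that "Any diagnosis of myocarditis or pericarditis is considered an important medical event and must be reported as an SAE".

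The Amendment 5 entry in Section 10.13 records the history: "Myocarditis and pericarditis are now considered AESIs for up to 6 weeks (previously 4 weeks) after vaccination". The stated reason is alignment with regulatory requirements for COVID-19 vaccines.

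**The concern.** For this diagnosis the protocol chose a strict rule: one confirmed case, related or not, pauses dosing in every group. It also chose to look for the diagnosis for 6 weeks. On days 29 to 42 the search continues but the automatic response does not.

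The other criteria (ECG or troponin findings, death, related Grade 4 events or SAEs, repeated related Grade 3 events) sit under the same 4-week lead-in, so none of them covers those days. A late case would still reach the sponsor and the IRC, but whether to pause would be a matter of judgement. At stake is whether participants not yet dosed are protected by rule or by discretion.

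**Working it through.** **1. The windows side by side**

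| Item | Substudy A | Substudy B |
|---|---|---|
| AESI window (8.4.7) | 4 weeks | 6 weeks |
| Cardiology evaluation of symptoms (10.11.8.8.10; 10.12.8.10 and 10.12.8.12) | 4 weeks | 6 weeks |
| Stopping-rule window (10.11.8.6; 10.12.8.7) | 4 weeks | 4 weeks |

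The three windows agree in Substudy A and differ only in Substudy B. The Substudy B summary of cardiac symptom data (protocol 10.12.9.3.5; Substudy B SAP 6.5) also stops at 4 weeks.

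**2. Length of the gap**

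6 × 7 − 4 × 7 = 42 − 28 = 14 days, that is, days 29 to 42 after vaccination. If vaccination is counted as Day 1, these are study Days 30 to 43, and the length is the same. This is calendar time, not a share of the risk.

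**3. How many people a pause could reach**

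The Section 1.2 schema footnote requires a sentinel safety review "with the exception of Groups 1, 3, 4, and 5, as enrollment of those groups occurred under a prior protocol version". From Table 8:

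- Groups 1, 3, 4 and 5: 30 + 3 × 120 = 390 places, enrolled under the prior version.
- Groups 2 and 6 to 12: 8 × 30 = 240 places.
- Total 390 + 240 = 630; 240/630 = 38.1%.
- After up to 10 sentinels per group: 8 × (30 − 10) = 160 places.

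**4. Chance of at least one case on days 29 to 42**

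The documents give no rate for this interval, so p below is an assumption. The number at risk is n = 240 if Group 12 is counted. It is 7 × 30 = 210 if not: the heading of 10.12.8.7 names Group 12, but its text describes combination vaccines, and Group 12 receives qIRV alone. The formula is 1 − (1 − p)^n.

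| Assumed p per participant, days 29 to 42 | n = 210 | n = 240 |
|---|---|---|
| 1 in 100,000 | 0.21% | 0.24% |
| 1 in 10,000 | 2.08% | 2.37% |

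For a 5% chance, p = 1 − 0.95^(1/n): 0.0244% (about 1 in 4,100) for n = 210 and 0.0214% (about 1 in 4,700) for n = 240.

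These are upper limits on the chance of an extra pause, because dosing must also still be open more than 4 weeks after the affected participant's dose.

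**The case against.** The strongest reply is that the windows serve different purposes. An AESI window governs reporting and signal review; a stopping window governs an automatic halt. The protocol does not match them elsewhere: SAEs, including deaths, are collected for about 6 months, yet death and related SAEs pause dosing only within 4 weeks. Four weeks is also the AE collection period and twice the typical 14-day onset in Section 2.3.1. Amendment 5, which lengthened the AESI window, also revised the stopping rules, so the 4 weeks may be deliberate. Late cases are not ignored: they are reported as SAEs within 24 hours, the sponsor is unblinded, and the IRC monitors safety throughout.

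Much of this stands as an argument about priority:

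- The documents do not show whether 4 weeks was an oversight or a choice. They give no reason for it.
- The IRC charter is not available here and may contain further triggers.
- Lengthening only this criterion leaves a related death on day 30 without an automatic pause. The difference is that this diagnosis is the one for which the protocol itself extended active work-up to 6 weeks.
- The figures of 240 people at risk and 240 places still protectable cannot both hold at once. The 160 describes the point when only sentinels are dosed, and their planned pause is 24 hours, not 4 weeks. Each figure is a ceiling, and together they do not estimate benefit.

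None of this supplies an automatic pause on days 29 to 42. The existing safeguards depend on discretion.

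**Conclusion.** The concern holds as a minor design point. In Substudy B the automatic one-case pause ends 14 days before the AESI and work-up windows for the same diagnosis, and no rationale is stated.

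The likely benefit of closing the gap is small. Late cases are improbable: at most about 0.2% to 2.4% for any such case, under assumed rates of 1 in 100,000 to 1 in 10,000. In a single-dose study a pause helps only those not yet dosed, at most 240 of 630 planned places. Cohorts may enrol at different times and no enrolment rate is given, so whether dosing would still be open cannot be determined. If dosing is complete, the change has no practical effect in this study.

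**What to change.** In Section 10.12.8.7, keep 4 weeks for the other criteria and add to the confirmed myocarditis or pericarditis criterion: *applies to any confirmed case, symptomatic or asymptomatic, with onset (first symptom or, if asymptomatic, first abnormal cardiac finding) within 6 weeks after vaccination, whenever confirmed.*

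This also settles whether onset or confirmation must fall inside the window, which matters because confirmation may need an echocardiogram or cardiac MR. The asymptomatic clause preserves present coverage. Routine ECG and troponin end at Visit 203 (days 6 to 8), so the added days mainly concern symptomatic cases. The 6-week AESI and work-up windows should not be shortened. If 4 weeks is intended, state the reason in 10.12.8.7 instead.

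The cost is one sentence in an amendment, with no new visits, tests or data, since SAEs are already collected for 6 months. The downside is that, without a relatedness test, one late and possibly unrelated case would halt every group still dosing until the IRC has reviewed it. The chance of that is bounded by the same 0.2% to 2.4%.
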